10.1.3. Missing and Partial Adverse Event Onset Dates

See Section [6.8.4](#).

10.1.4. Summaries of Adverse Event Incidence Rates per Person-Year of Exposure to Study Treatment

For this study, the duration of exposure to study treatment will vary depending on whether the subject is initially assigned to placebo. Because of this, certain AE tables will be repeated using the number of TEAEs per 100 person-years of exposure instead of using a count, where 1 year = 365.25 days of exposure. These tables will not be created for the Part 1 primary efficacy analysis since the same amount of exposure is expected per treatment group for Part 1 analysis.

To determine the rate of TEAEs per 100 person-years of exposure, the duration of treatment exposure will be computed for each subject and treatment. The rate of TEAEs per person-year will then be calculated as the count of TEAEs divided by the duration of treatment exposure. This value will then be multiplied by 100 to compute the rate per 100 person-years of exposure. For subjects initially randomized to placebo, there will be exposure time for placebo treatment and a separate exposure time for treatment with either 110 or 150 mg. The total exposure for the treatment group of interest will sum the individual subject exposure time for each treatment group.

The following summary tables of rate of TEAEs per 100 person-years of exposure will be provided by treatment group (by SOC and PT):

- Summary of TEAE rate per 100 person-years of exposure
- Summary of drug-related, TEAE rate per 100 person-years of exposure
- Summary of TESAEs per 100 person-years of exposure

A listing of person-years of exposure to study treatment will be provided by subject and treatment.

10.2. Exposure to Study Treatment and Treatment Compliance

The number of subjects exposed to study treatment, the number of subjects who discontinue treatment early, and the reasons for early discontinuation will be presented on the disposition table. A summary of exposure to study treatment will be also be presented and will include a summary of person-years of exposure to study treatment as described in Section 10.1.4. Listings of exposure to study treatment and of drug accountability will be provided by subject and treatment. KM plots of duration of study treatment will be provided. Treatment compliance will be computed based on drug accountability by determining the number of capsules taken relative to the number of capsules that should have been administered.

For compliance (%) for the study period of interest based on the drug accountability page of the eCRF:

$$\text{number of capsules taken} = \text{number of capsules dispensed} - \text{number of capsules returned}$$

$$\text{expected number of capsules taken} = 2 * (\text{date of the last dose} - \text{date of the first dose} + 1)$$

If the number of capsules taken per day changes due to formulation or lot changes at any time (eg, from 2 per day to 1 per day), the expected number of capsules will be adjusted accordingly at the date of the change.

Treatment compliance based on dispensing information will be calculated for each study treatment that the subject received as follows:

$$\text{Treatment compliance (dispensing)} = \frac{\text{Number of capsules taken}}{\text{Expected number of capsules taken}} * 100$$

Treatment compliance will be listed and summarized for Part 1 for all subjects and for Day 1 to Week 24, Day 1 to Week 48, and Day 1 to Week 52, for subjects who have completed the respective visit. For subjects initially assigned to placebo, treatment compliance will be computed for placebo treatment and separately for the active treatment received in Part 2.

A categorical summary of treatment compliance will be produced with the following categories shown in Table 15.

Table 15: Definition of Compliance Categories

Compliance	Range of Compliance (%)
Poor compliance	< 80%
Acceptable compliance	80% to < 90%
Good compliance	90% to 110%
Over-dosing	> 110%

A plot of CFB event rate by % compliance will be produced for Part 1, with treatment groups overlaid.

Treatment compliance will also be calculated between scheduled visits (or between the final dispense date and the final return date) similar to above with the following changes. The expected number of capsules will be computed as the number of capsules expected between scheduled dispense dates. Drug will be assumed to have been taken during the period after the

drug was dispensed, as long as the bottle is returned, regardless of the return date. Visits for which no bottles are returned at any time are considered missing data and compliance is not calculated in these cases. Note that this calculation does not take into account any protocol-allowable study drug interruptions.

10.3. Concomitant and Other Medications

Association of concomitant medications with treatment and coding of concomitant medications is described in Section 7.7. Concomitant medications will be summarized by treatment and WHO preferred name for Part 1 and for the entire study period. Multiple medication use (by preferred name) will be counted once only per subject. Concomitant medications started more than 30 days post last dose will not be included in summary displays but will be listed.

Concomitant medications that were used for HAE-related indications will also be summarized separately for Part 1 and for the entire study period.

All medication data will be listed.

10.3.1. Missing and Partial Concomitant and Other Medication Start and Stop Dates

See Section 6.8.3.

10.4. Laboratory Data

The following endpoint is a Part 1 safety endpoint and Part 2 primary endpoint:

- Number and proportion of subjects who experience a treatment-emergent Grade 3 or 4 laboratory abnormality

A listing of clinical laboratory evaluations is provided in the Protocol, Section 11.2.6.

Clinical laboratory assessments and corresponding changes from baseline will be summarized for each laboratory panel by treatment group and visit. Laboratory abnormalities will be graded according to the DMID Adult Toxicity Table (publish date: November 2007; see Protocol Appendix 16.1). Any graded abnormality that occurs following the initiation of study drug and represents at least one-grade increase from the baseline assessment is defined as treatment emergent.

Urinalysis results will be summarized by treatment and visit and listed by subject and treatment.

The number and percentage of subjects experiencing treatment-emergent graded toxicities will be summarized. Treatment-emergent Grade 3 or 4 laboratory abnormalities will be summarized separately. Laboratory toxicity shifts from baseline to worst postbaseline assessments will be summarized.

The number and percentage of subjects who have post-baseline elevations in liver transaminase (alanine aminotransferase [ALT] or aspartate aminotransferase [AST]) or bilirubin abnormalities in relation to fold above the upper limit of normal will be summarized according to the US Food and Drug Administration's (FDA's) Premarketing Clinical Evaluation on Drug-Induced Liver Injury Guidance for Industry (DHHS 2009).

The following categories of abnormal hepatic laboratory values will be evaluated for any occurrence among all post baseline assessments (where "and" indicates elevations occurring at the same visit). Within each treatment group and laboratory parameter grouping, a subject may

be counted once per elevation criteria using the worst-case result. That is, a subject with a worst-case ALT elevation $>3 \times$ the upper limit of normal (ULN) for a given treatment group would be counted once in the ALT $> 1.5 \times$ ULN category and once in the ALT $> 3 \times$ ULN category, regardless of how many ALT elevations the subject had that met the $> 3 \times$ ULN and $> 1.5 \times$ ULN elevation criteria.

- ALT and/or AST $> 3 \times$ ULN and total bilirubin > 1.5 or $2 \times$ ULN
- AST $> 1.5, 3, 5, 10,$ and $20 \times$ ULN
- ALT $> 1.5, 3, 5, 10,$ and $20 \times$ ULN
- Total bilirubin $> 1, 1.5,$ or $2 \times$ ULN
- Alkaline phosphatase (ALP) $> 1.5 \times$ ULN

The summary display of abnormal hepatic laboratory values will be repeated by prior use of androgens (yes/no) based on medical history. Detailed listings of prior androgen use will be provided for subjects with any elevation in the indicated categories.

Profiles of liver enzymes and bilirubin over time will be graphically displayed for subjects with any Grade 3 or 4 abnormality in these analytes. In addition, a listing of all liver function test (ALT, AST, bilirubin, ALP, gamma-glutamyl transferase) results for subjects experiencing a treatment-emergent Grade 3 or 4 liver function test will be provided.

In addition, a Hy's law plot, a shift plot showing liver safety panel tests over time (baseline vs. on-study), and distribution plots of ALT, AST, ALP, bilirubin, cholesterol, and triglycerides over time will be produced using the format recommended by the FDA/Industry/Academia Safety Graphics working group (<https://www.ctsmedia.org/do/view/CTSpedia/StatGraphHome>). The plots to be included are the scatter plot of maximum transaminase vs. maximum bilirubin, the liver test safety panel over time and the distribution of ALT by time and treatment. The distribution plots for AST, ALP, bilirubin, cholesterol, and triglycerides will use the same format as is used for ALT.

Separate KM plots of time to event for a Grade 3 or higher ALT, AST, or bilirubin will be produced.

A listing of AEs of nausea, vomiting, anorexia, abdominal pain, or fatigue occurring within 24 hours of an elevation of AST or ALT will be produced.

10.4.1. Prior Androgen Use and Liver Function Test Abnormalities

The summary display of abnormal hepatic laboratory values will be repeated by prior use of androgens (yes/no) at any time in the past based on medical history. Detailed listings of prior androgen use will be provided for subjects with any elevation in the indicated categories.

10.4.2. Complement Factors and HAE Diagnosis

Laboratory results related to HAE diagnosis, including complement factors C1-INH antigenic level, C1-INH functional level, complement 3 (C3), and C4 will be included in summaries of laboratory data. Criteria used to confirm diagnosis of HAE Type 1 or 2 will be summarized and listed as described in Section 7.4.

10.4.3. Laboratory Assessments for Rash

For subjects with rash, peripheral blood mononuclear cells will be collected for analysis of possible drug-specific immune responses and possible drug-responsive T cells.

Other laboratory assessments taken at the time of a rash, including clinical chemistry, hematology with differential, C3 level, and urine eosinophils will be included in laboratory listings.

10.5. Pregnancy

A listing of pregnancy test results will be provided.

10.6. Vital Signs

Vital signs (systolic and diastolic blood pressure, pulse rate, temperature, and respiratory rate) and body weight and corresponding changes from baseline will be summarized by treatment group and visit using descriptive statistics. These data will be listed by subject, treatment, and visit.

Distribution plots of systolic and diastolic blood pressure over time will be produced using the format recommended by the FDA/Industry/Academia Safety Graphics working group (<https://www.ctsmedia.org/do/view/CTSmedia/StatGraphHome>). The graph format to be used is the same as the graph provided for the distribution of ALT by time and treatment.

A scatter plot of baseline values vs. all observed changes relative to baseline recorded at any time will be produced.

10.7. 12-lead Electrocardiograms

Baseline (pre-dose) and Week 24 ECGs will be obtained in triplicate (ie, three separate readings) at 1- to 5-minute intervals, with baseline values calculated from an average of the 3 readings. All other ECGs will be single assessments.

An ECG should be repeated for a CFB in corrected QT interval using Fridericia's method (QTcF) > 60 msec or a QTcF interval > 500 msec.

ECGs and corresponding CFB will be summarized by treatment group and visit using descriptive statistics.

ECG findings will be summarized.

The CFB in QTcF will be determined by routine ECGs. At each time point where ECGs are analyzed, an individual subject's CFB will be calculated as:

$$\Delta_{ik} = (\text{QTcF for subject } i \text{ at time point } k - \text{Baseline QTcF})$$

QTcF measurements will be the average of triplicate ECGs at baseline and Week 24 and single values at all other time points.

A distribution plot of QTcF over time will be produced using the format recommended by the FDA/Industry/Academia Safety Graphics working group (<https://www.ctsmedia.org/do/view/CTSmedia/StatGraphHome>). The graph format to be used is the same as the graph provided for the distribution of ALT by time and treatment.

A scatter plot of baseline values vs. all observed changes relative to baseline recorded at any time will be produced.

For routine ECGs, the number and proportion of subjects with QTcF ≤ 450 , > 450 to ≤ 480 , > 480 to ≤ 500 , and > 500 msec; or changes of ≤ 30 , > 30 to ≤ 60 , or > 60 msec will be summarized. Unscheduled ECG results will be included in this summary table.

All ECG values and findings will be listed by subject, treatment, and visit.

10.8. Physical Examination

A full physical examination is conducted at Screening, Baseline, and at Week 24. Symptom-directed physicals are done at all other study visits except Week 2 and Week 26. Physical examination data will be listed by subject and treatment.

10.9. Study Termination Status

Study termination status will be presented on the subject disposition table.

11. PHARMACOKINETICS

Analyses of concentration data will be performed using the safety population. PK concentration data will be listed by subject, treatment, day, and time for Part 1 and for the entire study period at the end of Part 2. Note that PK concentration data collected at each visit will not be summarized by visit as the timing of PK data collected was not pre-specified.

The following summary displays will be produced:

- Summary of number and percentage of collected samples $> 4 \times$ half-maximal effective concentration (EC_{50}) $> 6 \times EC_{50}$, and $> 8 \times EC_{50}$ at each visit and overall
- Summary of number and percentage of samples within a subject $> 4 \times EC_{50}$, $> 6 \times EC_{50}$, and $> 8 \times EC_{50}$

The value of EC_{50} used will be 9 ng/mL.

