10.3.3.4. Week 24 Visit

The Week 24 visit will be conducted on Day 169, the day after the last dose of study drug in Part 1. Before any study drug for Part 2 is administered, the following assessments will be completed:

- Administration of EQ-5D-5L (1-2 questionnaires), AE-QoL, TSQM, and WPAI questionnaires. Where possible, the questionnaires should be completed by the subject prior to other assessments to prevent influencing subject perceptions.
- Subject weight
- Vital signs (blood pressure, temperature, respiratory rate, and pulse rate)
- 12-lead ECG (in triplicate)
- Complete physical examination
- Blood collection for clinical chemistry, hematology, and coagulation, troponin I and troponin T, NGAL, and CK-MB
- PK concentration and PD plasma samples
- Urine collection for urinalysis, possible reflex testing for abnormal GGT, AST, or ALT, and urine pregnancy test for all female subjects of childbearing potential. A negative urine pregnancy result must be recorded in order for the subject to be dosed.
- Review of concomitant medications and AEs
- Part 1 study drug collection/accountability

- e-diary instruction and review and set up. The e-diary should be turned to Part 2 at the conclusion of these assessments, prior to randomization and study drug dispensing for Part 2.

After completion of the above bulleted items at the conclusion of the visit, Part 2 study drug may be dispensed from the IXRS and accountability performed. The first dose of study drug in Part 2 may be administered (if timing coincides with typical dosing time, see Section 9.3.2). Study drug in Part 2, if not given at the visit, should be taken the day of the visit.

During the Part 2 dosing period, investigators will contact subjects to discuss details of all angioedema events recorded in the e-diary within approximately 2 business days of the end of the angioedema event. Moreover, any noncompliance will warrant contact with the subject.

10.3.4. Part 2

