11.2.12. Pharmacokinetics and Pharmacodynamics

All plasma samples for determination of BCX7353 will be analyzed using a validated liquid chromatography-mass spectroscopy assay. The analysis of PK concentration samples obtained from subjects randomized to placebo may be limited. The bioanalytical laboratory performing the analysis may be given the randomization scheme prior to unblinding to avoid analysis of subjects who received placebo.

Blood samples for PK and kallikrein inhibition will be drawn on all subjects at baseline and subsequent visits through Week 52 (except Weeks 2 and 26).

The samples ordinarily can be drawn at any time post-dose; however, during Part 1, at least 1 sample should be drawn at the approximate C_{max} of the drug, approximately 3 to 6 hours post-dose. Actual date and time of sample collection will be recorded in the eCRF. Sites will ensure that the time of the previous dose prior to the blood draw is recorded in the e-diary (may also be captured in the eCRF).

Instructions for collection, processing, storage, and shipment of PK and PD samples will be provided to the clinical site in a separate document.

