12. PHARMACODYNAMICS

Analyses of concentration data will be performed using the PD population. The baseline amidolytic activity mean will be summarized by treatment for all subjects and for males and females separately.

Plasma kallikrein inhibition (KKI) data will be expressed as percent inhibition compared to subject baseline activity (%KKI). The formula for percent inhibition is:

$$\%KKI = 100 - (\text{postbaseline value})$$

where the values are the mean amidolytic activity (%) at each time point. The mean amidolytic activity is set as 100% at baseline. Multiple assessments of amidolytic activity from samples at a single time point will be handled as described in Section 6.7.4.

%KKI data will be listed by subject, treatment, day, and time. This analysis will be conducted for Part 1 and then repeated for the entire study period.

The following summary displays will be produced:

- Summary of number and percentage of collected samples with > 50% and > 80% inhibition at each visit and overall
- Summary of number and percentage of samples within a subject with > 50% and > 80% inhibition

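### SAP 11 declines by-visit concentration summaries because draw time was not pre-specified, then plans by-visit threshold percentages of the same samples; visit is partly confounded with time since dose, most clearly at Week 24

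*SAP*

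**What the plan says.** SAP Section 11 gives the rule and its reason: "PK concentration data collected at each visit will not be summarized by visit as the timing of PK data collected was not pre-specified". The first display listed after it is the number and percentage of samples above 4, 6 and 8 times EC50, reported "at each visit and overall". The EC50 value "used will be 9 ng/mL".

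SAP Section 12 uses the same layout for the PD data: "Summary of number and percentage of collected samples with > 50% and > 80% inhibition at each visit and overall". It carries no remark on timing. Both sections also plan within-subject percentages. The SAP table list gives the threshold displays as Tables 14.5.2.1 and 14.6.2.1, and a separate concentration summary as Table 14.5.1.1.

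On sampling, Protocol Section 11.2.12 says: "The samples ordinarily can be drawn at any time post-dose; however, during Part 1, at least 1 sample should be drawn" near the expected peak, about 3 to 6 hours after dosing. Protocol Section 10.3.3.4 treats Week 24 differently: "The Week 24 visit will be conducted on Day 169, the day after the last dose of study drug in Part 1". It adds: "Before any study drug for Part 2 is administered, the following assessments will be completed". The PK and PD samples are on that list.

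**The concern.** Turning a concentration into above or below a threshold does not remove its dependence on when the blood was drawn. If untimed sampling is a reason not to show concentrations by visit, it is equally a reason not to show threshold percentages by visit.

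The sampling rules also differ between visits. Week 24 is tied to the period before that day's dose and the earlier on-treatment visits are not. A lower percentage at Week 24 could be read as waning exposure or waning kallikrein inhibition when it shows only a different draw time. Characterizing the PD effect is a Part 1 secondary objective. With about 8 subjects per arm, one subject moves a by-visit percentage by 1/8 = 12.5 points, so small imbalances in draw time would be visible.

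**Working it through.** **Step 1: are the two plans about the same data?** SAP Section 11 sets EC50 at 9 ng/mL. The thresholds are 4 × 9 = 36, 6 × 9 = 54 and 8 × 9 = 72 ng/mL. The by-visit percentages are therefore by-visit summaries of the concentrations that the section has just said will not be summarized by visit.

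**Step 2: do the visits differ in draw time by design?**

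- Weeks 4, 8, 12 and 18 (Protocol 10.3.3.3 and the Part 1 schedule footnotes): no dose is withheld, no clinic dose is required, and most samples need bear no relation to dosing.
- At least one Part 1 sample is aimed at 3 to 6 hours post-dose; the visit is not fixed.
- Week 24 (Protocol 9.4 and 10.3.3.4): last Part 1 dose on Day 168, visit on Day 169, samples before the Part 2 dose.

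Week 24 is thus the only on-treatment Part 1 PK/PD visit fixed before that day's dose. If the entire-study versions of these tables use SAP Table 9, placebo switchers' untimed Week 48 samples would also appear as adjusted Week 24, alongside the pre-dose Week 24 samples.

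**Step 3: could this matter numerically?** There is no figure in the plan to reproduce. The documents give no human half-life, peak-to-trough ratio, concentration or actual draw times, so everything in this step is an assumption that shows a range and is not an estimate.

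Assume log-normal concentrations with CV 50%, so σ = √ln(1 + 0.5²) = 0.472. An early sample is at 4.5 h and a late one at 24 h. The fraction left is r = 0.5^(19.5/half-life). For median M at 4.5 h and threshold T:

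- early share above T = Φ(ln(M/T)/σ)
- late share above T = Φ(ln(rM/T)/σ)
- gap between other visits and an all-late Week 24 = w × (early − late), where w is the share of other-visit samples that are early

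Example: M = 100 ng/mL, half-life 24 h, T = 54. Then r = 0.57, early = 90% and late = 54%, a difference of 36 points. With w = 0.5 the gap is 18 points.

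A value of w = 0.25 is what would result, on average over Weeks 4, 8, 12 and 18, if each subject gave exactly one early sample across those four visits (1/4).

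| M (ng/mL) | Half-life (h) | r | Gap, w = 0.25 (>4x / >6x / >8x) | Gap, w = 0.5 |
|---|---|---|---|---|
| 100 | 12 | 0.32 | 14 / 19 / 18 | 29 / 38 / 36 |
| 100 | 24 | 0.57 | 4 / 9 / 11 | 8 / 18 / 22 |
| 100 | 96 | 0.87 | 0 / 2 / 3 | 1 / 3 / 5 |
| 250 | 96 | 0.87 | 0 / 0 / 0 | 0 / 0 / 0 |

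With w = 0 the gap is 0 in every row. Over the full grid (M 60 to 250, half-life 12 to 96 h, w 0 to 1) it runs from 0 to 76 points. A range that wide shows that the assumptions, and not the documents, determine the answer.

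**The case against.** The strongest reply is that a real distortion may not exist. Dosing is with the subject's largest meal. Someone who doses in the evening and attends by day is sampled the next day, before dosing, at every visit, so Week 24 is no different for that person. If concentrations sit well above 72 ng/mL, or decline slowly, the percentages barely move whatever the draw time. This stands, and it is why no size is claimed.

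A reader might go further and infer that Week 24 will show a false loss of drug effect, or that its sample is always a trough. The documents support neither. They fix only that the sample precedes the first Part 2 dose; an evening doser seen the next morning is well short of 24 hours.

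SAP Section 12 does not contradict itself. The sentence ruling out by-visit summaries concerns concentrations only, so the PD point rests on the shared sampling rules. Protocol Section 13.4.2 calls for summaries by study visit, including concentration and PD results, so simply deleting the by-visit rows would move the SAP away from the protocol. Against that, Protocol Section 13.4.9 plans PD summaries by treatment, day and time, and time-banding serves that intention.

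Nor are these the only PD displays. Table 14.6.1.1, the within-subject percentages, the listings and the inhibition-versus-concentration scatter plot remain available.

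**Conclusion.** SAP Section 11 is internally inconsistent, and that rests on the text alone. The extension to SAP Section 12 is by implication. Visit and time since dose are partly confounded by the sampling rules, most clearly at Week 24, so a by-visit difference there could reflect draw time rather than a change in exposure or inhibition.

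Whether any such difference will appear, and how large it would be, cannot be derived from the documents. It may be zero. The displays are descriptive, no PD hypothesis is tested, and the efficacy analyses are unaffected. The point is a modest one, worth correcting because the remedy is cheap and the SAP already accepts the reason for it.

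**What to change.** In Tables 14.5.2.1 and 14.6.2.1, report the percentage above each threshold by time since last dose, in bands that cover the whole interval: for example <3 h, 3–6 h, >6–<18 h and ≥18 h. Keep the within-subject summaries. If by-visit rows are retained to match Protocol Section 13.4.2, label Week 24 as drawn before the Part 2 dose and footnote that draw times vary at the other visits.

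Reconcile the SAP Section 11 sentence with Table 14.5.1.1, a concentration summary whose layout the SAP does not show because the shells are kept separately (SAP Section 17.2).

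The cost is SAP wording and one derived variable. Protocol Section 11.2.12 already requires the sample time and the preceding dose time to be recorded, so no new data are needed. The drawback is sparse bands with about 8 subjects per arm, so counts should be shown beside the percentages.
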